4.10.3 Handling of Dropouts or Missing Data

With exception of some dates for the AEs calculation, missing data will not be imputed.

In case the end date of the treatment is known but the time is missing, then end time will be imputed with a time of 00:00.

The analysis based on mixed model for repeated measure (MMRM) will be performed using only the observed measurements without imputation of missing values.

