4.9.2 Treatment Compliance

Compliance will be assessed by checking the daily e-Diary and eCRF.

For all treatments, treatment compliance will be calculated as:

$$\text{Treatment compliance (\%)} = \frac{\text{Number of doses taken during treatment period}}{\text{Number of doses planned (28 days*) during treatment period}} \times 100.$$

*The number of doses planned is 55 since there is only 1 dose in the morning of Day 28.

Compliance is expected to be $\geq 80\%$ during the Treatment Period.

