- SOC and preferred term.
- SOC, preferred term, and maximum intensity.
- SOC, preferred term, and relationship to study intervention judged by investigator.

Adverse event summaries will be ordered in terms of decreasing frequency for SOC, and preferred term within SOC.

The tables of AE will include all the AEs with an onset date and time on or after the date and time of first dose of IP up to the end of treatment + 96 hours. Additional tables including all the AEs experienced after the IP until last follow-up (Day 56) and for ADA status will be reported for both Part 1 and Part 2.

Adverse events sorted by decreasing frequency and AEs leading to discontinuation of investigational product by SOC and preferred term will be summarised.

The number and percentage of subjects who experience 1 or more SAEs will be tabulated by treatment group (AZD1402 and placebo) and by SOC and preferred term and by SOC and preferred term and with outcome of death.

For each subject and each AE, the worst severity recorded will be attributed and used in the by-severity summaries. Similarly, the worst causality (most related to treatment) will be attributed and used in the by-causality summaries. If severity or causality is missing, a conservative approach for AE assessment (taking into account the worst case) will be followed.

Key subject information for participants experiencing SAE with outcome death, SAEs, and AEs leading to discontinuation of IP will be presented in a listing. All the AE will be included in the data listings.

Statistical Analysis Plan

For AEs with partial dates/times, worst case is always assumed; if possibly on-treatment, then on-treatment is assumed, on-treatment AEs will be considered to have the longest possible duration and off-treatment AEs will be considered to have the shortest possible duration. In accordance with this principle, any AEs with incomplete start and end dates/times will be treated as follows:

- AEs with unknown start times, but with start date known, will be imputed with a time of 00:00, unless the start date corresponds to any given dosing date. In this case the start time will be imputed with the time of dosing. If this results in a start date/time after end date/time of the AE, then the time will also be imputed with 00:00.

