Shift from baseline to maximum and to minimum on-treatment tables will be presented for laboratory parameters (chemistry, haematology and coagulation, urinalysis and immune biomarkers) including all blood white cells. The number of subjects with treatment emergent haematology abnormalities will be summarised.

The criteria for the haematology treatment emergent abnormalities (respect to baseline) are:

- Confirmed leucocyte count $< 2.0 \times 10^9/L$
- Confirmed neutrophil count $< 1.0 \times 10^9/L$
- Confirmed platelet count $< 75 \times 10^9/L$
- Confirmed lymphocyte count $< 0.5 \times 10^9/L$

Shift tables for the immune biomarkers IFNg, IL-10, IL-12p70, IL-13, IL-1b, IL-2, IL-4, IL-6, IL-8, TNFa, CRP, and IgE, will be presented by treatment and separately for each part.

Individual subject data where alanine aminotransferase/transaminase (ALT) and/or aspartate aminotransferase/transaminase (AST) and total bilirubin are elevated at any time will be listed (ie, ALT and/or AST $\geq 3 \times$ the upper limit of normal [ULN] and total bilirubin $\geq 2 \times$ ULN, at any time) to evaluate potential Hy's Law cases.

A figure for both ALT and AST versus total bilirubin expressed as multiple of ULN will be presented. Plot will be produced on the log scale, and reference lines will be included at $2 \times$ ULN for total bilirubin and at $3 \times$ ULN for ALT/AST.

Clinical laboratory data will be reported in the units provided by the clinical laboratory for the SRC meeting (if applicable), and in System International units in the CSR.

The number and percentage of subjects with a change from baseline in hsCRP higher than 5 and 10 mg/dL will be also reported by specified ADA status.

Figure for hsCRP over time by ADA status and by treatment group will be presented.

Statistical Analysis Plan

On-treatment and treatment emergent definition refer all the assessments with an onset date and time on or after the date and time of first dose of IP up to the end of treatment + 96 hours.

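### A missing end-of-treatment time set to 00:00 falls before that day's dose, so the +96-hour on-treatment safety window closes early; the practical effect is small and one value fixes it.

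*SAP*

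**What the plan says.** SAP 4.10.3 opens with a general rule: "With exception of some dates for the AEs calculation, missing data will not be imputed". It then adds an exception for treatment end. If the date is known and the time is not, "then end time will be imputed with a time of 00:00".

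That time matters because the safety windows are cut by clock time. SAP 4.17.2 states: "On-treatment and treatment emergent definition refer all the assessments with an onset date and time on or after the date and time of first dose", and the window runs "up to the end of treatment + 96 hours". SAP 4.17.3 (vital signs) and 4.17.4 (ECG) use the same limit, as do the main AE tables in 4.17.1.

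For AEs with incomplete timing, SAP 4.17.1 leans the other way: "For AEs with partial dates/times, worst case is always assumed; if possibly on-treatment, then on-treatment is assumed". An unknown AE start time on a known date becomes 00:00, or the dosing time if the date is a dosing date. The section gives no rule for an unknown treatment end time. It does plan further AE tables without the 96-hour limit, covering everything after first dose to Day 56.

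**The concern.** A participant cannot have finished treatment before inhaling the last dose, yet 00:00 on the last-dose date implies exactly that. The error has one direction: it can only close the window early, never late. Records that fall within 96 hours of the true last dose can therefore be classed as off-treatment and left out of the on-treatment safety summaries. For a safety window that direction is anti-conservative, and it sits badly with the stated intent of 4.17.1.

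The rule also has little other visible use. Exposure duration in SAP 4.9.1 is computed from dates alone. The +96-hour windows are the summaries in the SAP that need a clock time for the end of treatment.

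**Working it through.** **Inputs**
- Imputed end time: 00:00 on the known end date (SAP 4.10.3).
- Window after end of treatment: 96 h, by date and time (SAP 4.17.1 to 4.17.4).
- Planned last dose for a completer: a single morning dose on Day 28. SAP 4.9.2 says "The number of doses planned is 55 since there is only 1 dose in the morning of Day 28", which checks: 27 × 2 + 1 = 55.
- Clock time *t* of the last dose: not given, so assumed. I use 06:00 to 11:00 for a morning dose, and any time up to 23:59 for someone who stops earlier. End of treatment is taken to be the last dose.

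**Check of the plan's own figure.** A Day 28 dose at time *t* plus 96 h is Day 32 at time *t*. This agrees with the Part 1 schedule, which times the Day 32 pharmacokinetic (PK) sample at 96 h after the Day 28 dose.

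**Hours lost.** True close = end date + *t* + 96 h. Close under the rule = end date + 00:00 + 96 h. The difference is *t*.

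| True last dose | Hours lost | Hours left after dose | Share of 96 h |
|---|---|---|---|
| 06:00 | 6 | 90 | 6.3% |
| 08:00 | 8 | 88 | 8.3% |
| 11:00 | 11 | 85 | 11.5% |
| 20:00 | 20 | 76 | 20.8% |
| 23:59 | 23.98 | 72.02 | 25.0% |

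**Which records can move.** Only those dated end date + 4 days, between 00:00 and *t*.
- *AE with a known onset time.* Take a last dose at 20:00 with no recorded time, and an onset at 05:00 on end date + 4. The interval is 4 + 72 + 5 = 81 h, inside 96 h, but the rule classes the event as off-treatment.
- *AE with a missing start time.* Its start is set to 00:00 on end date + 4, the instant the shortened window closes. If the limit is inclusive, the classification is the same as with the true dose time. If it is exclusive, the event is dropped.
- *Laboratory, vital-sign and ECG records.* A discontinuation or unscheduled visit must fall in that band. In Part 2, protocol 7.1.1 asks for the discontinuation visit as soon as possible after the last intake, so this can happen.

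**Effect of 23:59.** The window closes at 23:59 on end date + 4, so it is never shorter than 96 h after the true dose. The overshoot is 23:59 minus *t*: 17 h 59 min for 06:00, 15 h 59 min for 08:00 and 12 h 59 min for 11:00.

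**The case against.** The strongest reply is that the rule has very little to act on, and most of that reply stands.

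- **Dose times should exist.** Protocol 6.4 has clinic doses witnessed, with date and time entered in the eCRF. In Part 2, home dose dates and times go into the e-Diary. The rule applies only where that capture fails.
- **Little scheduled data lies in the lost band.** In Part 1 the last scheduled ECG is on Day 28, and routine blood safety samples fall on Days 28 and 30, inside the window even under 00:00. In Part 2, Visit 8 is planned one to two weeks after Visit 7, past 96 h whichever time is used.
- **AEs are not lost.** They remain in the tables to Day 56 and in the listings, and the rule is the same in every arm.
- **23:59 is also inexact.** For an 08:00 dose it is about 16 h late, where 00:00 is 8 h early. This is true, but its error goes the way 4.17.1 already prefers.

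A reader might also infer that completers in Part 1 lose their whole Day 32 visit, where vital signs are scheduled. The documents do not support that. The Day 28 dose is a supervised clinic dose and the anchor for PK samples, so its time should be known and the imputation should rarely be triggered. The Day 32 PK sample also carries a tolerance of ± 2.5 h, so it can fall beyond 96 h even with a fully recorded dose time.

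**Conclusion.** The point holds as a minor one. Whenever the rule is applied, it places the end of treatment before the last dose and shortens the 96-hour window by that dose's clock time: about 6 to 11 h under the assumed morning times, and just under 24 h as a ceiling. The ceiling needs a late-evening last dose in an early discontinuer. It is not a typical loss, because the last planned dose is a morning dose.

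A reader might infer that 4.10.3 contradicts the worst-case rule in 4.17.1. That goes too far. The rule is worded for AEs with partial dates or times and is silent on treatment end. On an inclusive reading of the 96-hour limit, the AEs with a missing start time keep their classification. The conflict is with the principle: an AE with a known onset that was possibly on-treatment is classed as off-treatment.

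The practical effect is probably confined to early discontinuers with a home last dose and no recorded time, and to AEs or unscheduled or discontinuation-visit assessments on end date + 4 days. The documents do not say how often a time will be missing, so no count can be given. The SAP states no Day 56 counterpart for the on-treatment laboratory, vital-sign and ECG summaries, so a record cut there would appear only in listings or by-visit output. No efficacy result changes.

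**What to change.** In SAP 4.10.3, impute a missing end-of-treatment time as 23:59 of the known end date. Alternatively, define the on-treatment window in 4.17.1 to 4.17.4 as end date + 4 calendar days. SAP 4.8 already counts in days for medications, using treatment completion plus 4 days. Both options close the window at the end of the same day. It would help to state whether the limit is inclusive.

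The cost is one value in the SAP and the program, or one reworded definition. The downside is the overshoot of about 13 to 18 h beyond 96 h for a morning last dose. If only the imputed value is changed, this affects only participants with a missing time; a calendar-day window would extend it to everyone.

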4.10.4 Multiple Comparisons/Multiplicity

No adjustments for multiple testing will be performed.

4.11 Primary Efficacy Variable (Part 2)

The primary variable for the assessment of efficacy for Part 2 is the change from baseline pre-bronchodilator in-clinic FEV₁ at Week 4.

The change from baseline in pre-bronchodilator FEV₁ will be analysed using MMRM with treatment group, week (1 to 4), country, baseline FEV₁, and treatment-by-week interaction as fixed effects and with participant as random effect. In this model, Week 1 to Week 4 corresponds to Visit 4 to Visit 7.

The within participant correlation will be modelled using the unstructured covariance matrix. The Kenward-Roger approximation will be used to estimate the degrees of freedom. The REML method will be applied.

If the estimating algorithms will not converge, the following steps will be taken to simplify the model until convergence is achieved:

1. As a first step, try in order these 3 covariance structures: Toeplitz, the first-order autoregressive, and compound symmetry. Stop as soon as convergence is achieved.

Statistical Analysis Plan

2. If step 1 does not work, the treatment-by-week interaction will be removed from the last model in step 1, ie, from the model with compound symmetry.
3. In case non-convergence persists, the analysis will be changed to use the analysis of covariance (ANCOVA) instead of mixed-effects model for repeated measures.

Each treatment effect and treatment comparisons (all active treatments to placebo) will be estimated by the Least Square means (LS means) and the difference in LS means at the corresponding week (Week 1, Week 2, Week 3, Week 4) on the treatment-by-week interaction, along with their standard errors (SE) and 95% CIs, and the p-value corresponding to the between-treatment group difference. A plot showing the LS mean change (+/- SE) from baseline in FEV₁ over time within each treatment group will be provided.

Missing values will not be imputed. In this analysis it is thus assumed that any missing FEV₁ values are missing at random.

A listing of the primary efficacy data will be provided based on the FAS.

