9.4 Statistical Analyses

The SAP will be finalised prior to first participant in and will include a more technical and detailed description of the statistical analyses described in this section. This section is a summary of the planned statistical analyses of the most important endpoints including primary and key secondary endpoints.

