9.4.2.1 Primary Endpoint

The primary efficacy endpoint for Part 2 (Main Cohort) is the change from baseline in pre-bronchodilator FEV₁ at Week 4 compared to placebo.

The change from baseline in FEV₁ will be analysed using MMRM with treatment group, week (1 to 4), country, eosinophil count group (< 300, \geq 300 cells/ μ L), baseline FEV₁, and treatment-by-week interaction as fixed effects with participant as random effect. In this model, Week 1 to 4 corresponds to Visit 4 to 7. The within-participant correlation will be modelled using the unstructured covariance matrix. The Kenward-Roger approximation will be used to estimate the degrees of freedom.

Baseline for FEV₁ will be defined as the mean of the 2 measured values before first study intervention administration (30 minutes apart, at -45 minutes and -15 minutes, before study intervention) on Day 1.

Besides the main analysis in the FAS, treatment effect in primary endpoint will be evaluated in subgroups defined by measurements of eosinophil count (< 300 and \geq 300 cells/ μ L), and of FeNO (< 50 and \geq 50 ppb) evaluated at Day 1 pre-dose.

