9.4.2.2 Secondary Endpoints

Secondary efficacy endpoints for Part 2 (Main Cohort) will include:

- Change from baseline in pre-bronchodilator FEV₁ average over the 4-week Treatment Period
- Change from baseline in ACQ-6 at Week 4 and average over the Time Period
- Change from baseline in average morning PEF over the Treatment Period
- Change from baseline average evening PEF over the Treatment Period

- Change from baseline in daily average asthma symptoms score (AM/PM) over the Treatment Period
- Change from baseline in FeNO at Week 4 and average over the Treatment Period (analysed on natural log scale and results back transformed to linear scale).

Similar MMRM as for the primary variable will be used for analysis of change from baseline in ACQ-6 and in FeNO. Analysis of covariance with treatment and country as fixed effects, and baseline as covariate will be used for the analysis of change from baseline in average PEF.

Further details on the models for secondary endpoints will be provided in the SAP.

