This Statistical Analysis Plan (SAP) details the statistical methodology to be used for analysing the study data and outlines the statistical programming specifications for the tables, figures, and listings (TFLs). It describes the variables and analysis sets, anticipated data transformations and manipulations and other details of the analyses not provided in the Clinical Study Protocol (CSP). The SAP describes the statistical analysis as it is foreseen when the study is being planned. If circumstances should arise during the study rendering this analysis inappropriate, or if in the meantime improved methods of analysis should come to light, different analyses may be performed. Any deviations after database lock, reasons for such deviations and all alternative or additional statistical analyses that may be performed, will be described in a SAP addendum and discussed in the Clinical Study Report (CSR). Any changes to this SAP prior to database lock will be described in a new version of the SAP.

The following endpoints will be reported outside of the CSR and are therefore outside of the scope of this SAP:

- **CCI** **███████████**
- **CCI** **███████████**
- **CCI** **███████████**

The analyses described in this SAP are based upon the following study documents:

- Study Protocol, Version 8.0 (24 March 2023).
- Annotated Case Report Form 1.0 (21 January 2021).
- Annotated Case Report Form updates 7.0 (16 February 2023)

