- In-clinic post-bronchodilator ratio FEV₁/FVC (%).

Baseline lung function data to be assessed for Part 2 include:

- In-clinic FEV₁ in absolute value (L)
- In-clinic FeNO (part per billion [ppb]) (geometric mean and geometric coefficient of variation [GeoCV (%)] will be presented instead of mean and SD for this variable).

Baseline diary data to be assessed for **CC1** Part 2 include:

- ACQ-6 score

Baseline diary data to be assessed for Part 1 include:

- Cough VAS (mm)

Baseline diary data to be assessed for Part 2 include:

- Morning PEF (L/min).
- Evening PEF (L/min).
- Daily asthma symptom score.

The daily values of rescue medication use and of asthma symptom scores are calculated as the mean of the evening measurement for day n and the morning measurement for day n + 1.

Additional baseline assessments to be assessed for Part 1 and Part 2 include:

- Eosinophils count (10⁹/L).
- hsCRP (mg/L).

Additional baseline assessments to be assessed for Part 2 include:

- Eosinophils count group (cells/ μ L): < 300, \geq 300.

The baseline assessments detailed above will be summarised by treatment group (each dose level of AZD1402, placebo, and pooled AZD1402) and overall.

By-participant listings of demographics, participants characteristics, asthma history will be provided for the randomised subjects. For weight, height and BMI, and asthma exacerbation the listings will be presented for the safety set. All listings will be presented for each study Part.

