4.10.1 Analysis and Data Conventions

No statistical hypotheses will be tested in Part 1 (Lead-in Cohort) of this study. Part 2 (Main cohort) of this study aims to demonstrate that AZD1402 improves FEV₁ compared to placebo.

The null hypotheses for the primary analysis in Part 2 is that there is no difference in the change from baseline at Week 4 (Visit 7) in pre-bronchodilator in-clinic FEV₁ in AZD1402 treated participants compared to placebo-treated participants.

The following comparisons will be performed:

- AZD1402 inhalation ^{CCI} mg ^{CCI} versus placebo inhalation ^{CCI}.
- AZD1402 inhalation ^{CCI} mg ^{CCI} versus placebo inhalation ^{CCI}

4.10.2 No formal comparisons between the different AZD1402 doses will be conducted. Adjustments for Covariates

The primary efficacy analysis for Part 2 will be adjusted for the following baseline covariates:

1. Country (stratification variable)
2. Baseline FEV₁

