4.12.4 Fractional Exhaled Nitric Oxide

The analysis of change from baseline in log transformed FeNO will be performed as described for the primary endpoint in Section 4.11. These analyses will be done on the natural log scale and the results will be back-transformed to linear scale. Hence treatment effects will be presented in terms of Geometric LS means (GeoLSMeans) and treatment differences and associated CIs will be presented in terms of GeoLSMeans ratios. Due to the log-transformation, the GeoLSMeans represent a relative change from baseline rather than an absolute change from baseline.

Percentage change from baseline in FeNO at each week and average over the treatment period will be summarised by treatment group and the following summary statistics will be presented: n, geometric mean, GeoCV (%), median, minimum, and maximum.

For repeated follow-up post-baseline measurements that are taken on the same day and time as a scheduled visit and time point, the average response value of the morning assessments will be used. The average over the treatment period will be calculated from the subjects' average measurements of all assessments performed whilst subjects are on-treatment between Visit 3 and Visit 7.

All the efficacy variables will be presented in listings.

The following figures will be presented:

[figure not shown]
- In-clinic FeNO, individual subject data over time.
- Mean FeNO in-clinic absolute values (ppb) by week
- Mean FeNO in-clinic percentage change from baseline by week
- GeoLSMeans of the ratio (post/baseline) (+/- SE) in FeNO over time within each treatment group will be provided.

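### The SAP drops the eosinophil group from the protocol's primary FEV₁ model and replaces the protocol's ACQ-6 MMRM and PEF ANCOVA with summaries by arm, and records neither change

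*SAP*

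**What the plan says.** **Primary endpoint.** Protocol 9.4.2.1 analyses change in pre-bronchodilator FEV₁ by "MMRM with treatment group, week (1 to 4), country, eosinophil count group" (below 300, or 300 and above, cells/µL), with baseline FEV₁ and treatment-by-week interaction. SAP 4.11 specifies "MMRM with treatment group, week (1 to 4), country, baseline FEV₁, and treatment-by-week interaction as fixed effects". SAP 4.10.2 opens with "The primary efficacy analysis for Part 2 will be adjusted for the following baseline covariates" and lists two: country and baseline FEV₁. SAP 4.6 still derives the eosinophil group, but only as a Part 2 baseline characteristic.

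**Secondary endpoints.** Protocol 9.4.2.2 states: "Similar MMRM as for the primary variable will be used for analysis of change from baseline in ACQ-6 and in FeNO". It also prescribes an ANCOVA with treatment, country and baseline for change in average PEF. SAP 4.12.2 (ACQ-6) and 4.12.3 (morning and evening PEF) describe summaries by treatment group, with a pooled AZD1402 column; 4.12.2 adds a listing and responder counts. By contrast, SAP 4.12.1 gives average FEV₁ an LS-mean difference with CI and p-value. For FeNO, SAP 4.12.4 says: "The analysis of change from baseline in log transformed FeNO will be performed as described for the primary endpoint in Section 4.11".

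**Which protocol applies.** The SAP names "Study Protocol, Version 8.0 (24 March 2023") among the documents on which it is based.

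**Recorded changes.** SAP 4.20 lists removal of some exploratory endpoints, the Per Protocol analysis and the subgroup analysis, because closure was anticipated. The Final 5.0 entry in the revision history repeats these and adds AE, ADA and hsCRP outputs.

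**The concern.** ACQ-6 and PEF carry the larger consequence. Both documents list them as secondary endpoints for efficacy against placebo. An analyst who follows SAP 4.12.2 and 4.12.3 to the letter produces means by arm and no estimated difference, although the protocol promised a modelled one.

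For the primary endpoint, the protocol and the SAP prescribe different models and give no reason. A reader of the report could not tell whether the covariate was left out by decision or by oversight, or which model was the pre-specified one.

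The ACQ-6 responder definition is also inconsistent within the SAP. Section 3.2.1 fixes it at Week 4 (Visit 7). Section 4.12.2 speaks of the whole treatment period, which could mean any visit, the average or the last visit.

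**Working it through.** **1. Primary model, term by term**

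| Term | Protocol 9.4.2.1 | SAP 4.11 |
|---|---|---|
| Treatment, week, treatment-by-week | yes | yes |
| Country | yes | yes |
| Baseline FEV₁ | yes | yes |
| Eosinophil group | yes | no |

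SAP 4.10.2 agrees with SAP 4.11, so the omission is not a slip in a single line. The FeNO model in SAP 4.12.4 inherits it. The protocol asks only for a similar MMRM there, so FeNO is not counted as a separate departure.

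**2. Secondary efficacy items in SAP 3.2.1**

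| Item | Model named in Protocol 9.4.2.2 | SAP 4.12 |
|---|---|---|
| FEV₁ average | none | difference, CI and p-value from the 4.11 model |
| ACQ-6 change | MMRM | summary by arm |
| ACQ-6 responders | none | counts by arm |
| Morning PEF | ANCOVA | summary by arm |
| Evening PEF | ANCOVA | summary by arm |
| Daily symptom score | none | summary by arm |
| FeNO | MMRM | MMRM |

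The protocol names a model for 4 of 7 items. The SAP models 1 of those 4 and summarises the other 3.

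**3. Is it recorded?** The listed removal of the subgroup analysis does not cover the covariate: Protocol 9.4.2.1 sets out the main model and then describes subgroup evaluation as something additional. The Final 3.0 entry mentions alignment with protocol versions 5.0 and 6.0, updated standards, baseline definitions and two dropped post-bronchodilator endpoints. Final 4.0 mentions only alignment with version 7.0. No entry mentions the covariate, ACQ-6 or PEF.

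**4. Size of the covariate omission**

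Inputs from SAP 4.19: 73 evaluable per arm, 175 mL, one-sided 5%. Power, SD and correlation are redacted, so the 73 cannot be reproduced. Working backwards with SD = 175 / [(1.645 + z_β) × √(2/73)], it corresponds to an SD of 425.2 mL at an assumed 80% power, or 361.3 mL at an assumed 90%. The loss below does not depend on which of these SDs applies.

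Let R² be the assumed share of residual variance explained by the eosinophil group, and let the assumed power refer to the model that includes it. Omitting the group gives:

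- variance factor 1/(1 − R²)
- CI width factor 1/√(1 − R²)
- effective n per arm 73 × (1 − R²)
- power Φ[(1.645 + z_β) × √(1 − R²) − 1.645]

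| R² (assumed) | Variance factor | CI width factor | Effective n per arm | Power from 80% | Power from 90% |
|---|---|---|---|---|---|
| 1% | 1.010 | 1.005 | 72.3 | 79.65% | 89.74% |
| 3% | 1.031 | 1.015 | 70.8 | 78.93% | 89.20% |
| 5% | 1.053 | 1.026 | 69.3 | 78.19% | 88.64% |

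The losses are 0.35, 1.07 and 1.81 points from 80%, and 0.26, 0.80 and 1.36 points from 90%.

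**The case against.** Several points can fairly be made for the plan.

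- **The protocol calls its statistical section a summary and hands over to the SAP.** What it hands over is limited. Protocol 9.4 says the SAP "will include a more technical and detailed description of the statistical analyses described in this section", and 9.4.2.2 leaves it further detail on the secondary models. Deleting a named model is not adding detail.
- **SAP 1 allows different analyses if circumstances change, with changes before database lock described in a new version.** Final 5.0 is such a version. It does not describe these changes.
- **SAP 4.2 has a default: where no model estimates a treatment difference, an unadjusted CI is used, and nominal p-values may be shown.** That sets the type of interval once a difference is reported. It does not call for a difference in ACQ-6 or PEF, and 4.12.2 and 4.12.3 name none. The table shells, to which 4.2 refers other output details, were not available, so the point concerns the SAP text only.
- **SAP 4.2 provides summaries by timepoint as appropriate, so a Week 4 summary of ACQ-6 change is arguably covered even though 4.12.2 never names Week 4.** This stands for the change score. It does not resolve the responder wording.
- **The covariate effect is small, and descriptive secondary outputs can be defended in a Phase IIa study that expects to close early.** Both are accepted. They argue for a short recorded justification, which is what is missing.

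**Conclusion.** The point holds on the text of the two documents and should be fixed. The primary models differ by one covariate. Three protocol-named secondary analyses have become summaries by arm without a placebo comparison. The ACQ-6 responder window contradicts the SAP's own endpoint definition. None of this is listed among the changes.

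The lost ACQ-6 and PEF comparisons are the substantive part. Omitting the eosinophil group does not bias a randomised comparison; on its own it is mainly a matter of reconciling the documents, worth at most 1.81 power points across the range examined. That figure rests on an assumed R² of 1% to 5%, an assumed power of 80% or 90% and the planned 73 per arm, which early closure may mean was not reached. Earlier SAP versions were not available, so nothing is claimed about when the mismatch arose.

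**What to change.** Take one of two routes for each departure.

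**Bring the SAP into line with the protocol:**
- Add eosinophil group to SAP 4.10.2 and 4.11, and so to 4.12.4.
- In 4.12.2, specify the ACQ-6 MMRM with baseline ACQ-6 as covariate and contrasts against placebo at Week 4 and on average.
- In 4.12.3, specify the ANCOVA for morning and evening PEF with treatment, country and baseline. Report the difference from placebo with a 95% CI for these and for ACQ-6.

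**Or keep the departure** because of early closure, and list it with its reason in SAP 4.20.

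Under either route, define ACQ-6 responders at Week 4 (Visit 7) in 4.12.2. By the SAP's own rule in Section 1, changes before database lock go into a new version; later ones go into an addendum and are discussed in the CSR.

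The cost is low. The eosinophil group is already derived, the FEV₁ and FeNO MMRM code can be reused, the primary model gains one parameter, and a few tables are added. Keeping the departures costs a few lines in 4.20.

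### If the unstructured fit fails, SAP 4.11 tries only equal-variance covariance structures before its final ANCOVA step, so the Week 4 standard error becomes approximately a pooled Weeks 1–4 value

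*SAP*

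**What the plan says.** SAP 4.11 defines the primary variable as "the change from baseline pre-bronchodilator in-clinic FEV₁ at Week 4". The model has treatment, week, country, baseline FEV₁ and treatment-by-week as fixed effects, and participant as a random effect. On covariance it says "The within participant correlation will be modelled using the unstructured covariance matrix", and on estimation "The Kenward-Roger approximation will be used to estimate the degrees of freedom. The REML method will be applied". The Week 4 difference, its standard error, 95% CI and p-value are read from the treatment-by-week LS means. No robust (sandwich) standard error is named.

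For non-convergence, SAP 4.11 sets out three steps:

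1. "try in order these 3 covariance structures: Toeplitz, the first-order autoregressive, and compound symmetry", stopping at the first that converges.
2. If none converges, "the treatment-by-week interaction will be removed from the last model in step 1, ie, from the model with compound symmetry".
3. If that also fails, "the analysis will be changed to use the analysis of covariance (ANCOVA) instead of mixed-effects model for repeated measures". The time point and covariates of this ANCOVA are not given.

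Protocol 9.4.2.1 says "The within-participant correlation will be modelled using the unstructured covariance matrix" and gives no fallback, so the SAP sequence is the only rule. SAP 4.12.4 analyses log-transformed FeNO in the same way as 4.11, so that analysis inherits it.

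**The concern.** An unstructured matrix gives Week 4 its own variance. Toeplitz, first-order autoregressive and compound symmetry, as named, each have one variance common to all weeks. A participant random intercept adds the same constant to every week, so it does not relax this. Once step 1 is reached, the uncertainty of the Week 4 contrast is judged partly from the spread at Weeks 1 to 3. Kenward-Roger adjusts for small samples. It does not correct a variance model that is wrong.

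At stake are the standard error, CI and p-value of the primary comparison. If the spread grows towards Week 4, the interval is too narrow and the test too liberal. If it shrinks, the interval is too wide and power is lost. SAS 9.4, the stated software, offers all three structures with week-specific variances, and the SAP names none of them.

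**Working it through.** **Inputs from the documents.** SAP 4.19 gives 73 evaluable participants per arm, a difference of 175 mL and a one-sided 5% test. SAP 4.2 gives two-sided 95% CIs. There are four post-baseline weeks. Power, SD, between-week correlation and dropout rate are redacted. No SD by week appears anywhere.

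**The plan's own figure.** With n = 2·SD²·(1.645 + z_power)²/175² and n = 73, SD = 175·√(73/2)/(1.645 + z_power) = 1057.3/(1.645 + z_power). This gives about 425 mL at 80% power and 361 mL at 90%. The step from 73 to 80 implies 1 − 73/80 = 8.75% dropout. The sizing is therefore plausible but cannot be verified, and the present point does not depend on it.

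**Effect of the fallback.** Assume complete data and a separate mean for each treatment and week, ignoring baseline and country. The Week 4 estimate is then the same under every structure; only its standard error changes. Under compound symmetry the fitted common variance is the mean of the four weekly variances, so

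- SE ratio = √[(s₁² + s₂² + s₃² + s₄²)/4] / s₄
- actual one-sided error = 1 − Φ(1.645 × ratio)
- CI coverage = 2Φ(1.96 × ratio) − 1

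Fitting Toeplitz and AR(1) numerically gives the same ratio within 0.3% for Week 4/Week 1 SD ratios from 0.7 to 1.5, with a true correlation that is exchangeable (0.5 or 0.7) or autoregressive (0.7).

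**Worked cases** (weekly SDs assumed, linear in week):

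- 360, 380, 400, 420 mL: √(610,400/4) = 390.6; 390.6/420 = 0.930; error 6.3%, coverage 93.2%.
- 440, 420, 400, 380 mL: √(674,400/4) = 410.6; 410.6/380 = 1.08; error 3.8%.

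| Assumed Week 4/Week 1 SD ratio | SE ratio | One-sided error | CI coverage |
|---|---|---|---|
| 0.8 | 1.13 | 3.2% | 97.3% |
| 1.0 | 1.00 | 5.0% | 95.0% |
| 1.1 | 0.955 | 5.8% | 93.9% |
| 1.2 | 0.919 | 6.5% | 92.8% |
| 1.3 | 0.889 | 7.2% | 91.9% |

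**Simulation check.** With 73 per arm, exchangeable correlation 0.6 and 3,000 runs (simulation error about 0.4 points), one-sided error was:

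- SD ratio 1.3: 6.5% to 6.6% under the fallback structures, 4.6% under unstructured.
- SD ratio 0.8: 2.9% against 4.6%.
- Equal SDs: 5.6% against 5.5%.

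The direction matches the formula. At a ratio of 1.3 the simulated error is somewhat below the large-sample 7.2%.

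**The case against.** The strongest reply is that two conditions must both hold, and the documents show neither. First, the unstructured fit must fail. It has 4 × 5/2 = 10 covariance parameters with about 80 participants in each main arm, and would usually converge. Second, the weekly SDs must differ materially. Nothing in the documents says they do, and SAP 4.19 sizes the trial with one SD and one correlation. This stands, and it limits the weight of the point.

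The first condition is not fanciful, however. A participant random effect on top of an unstructured matrix is redundant, and coded literally it may itself prevent convergence. SAP 4.20 also anticipates early closure, so the achieved numbers may be smaller than planned. For this reason a remedy that only lengthens the list of structures would miss the likeliest cause of failure.

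It can also be said that this is a Phase IIa trial, without multiplicity adjustment, whose SAP (4.2) urges caution in reading CIs and p-values. A shift of one or two points in a contingency branch is unlikely to decide anything alone. That is fair, and it makes this an improvement rather than a correction the plan cannot do without.

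A reader might infer that the primary test is anti-conservative. The documents do not support that: the planned model is unaffected, and in the fallback the error may lie on either side of 5%. Nor do they support saying that every fallback pools the variance. An ANCOVA run on Week 4 data would not; the SAP leaves its time point open.

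**Conclusion.** The point holds as a conditional weakness in a stated rule. If the unstructured model fails, every covariance structure tried in step 1 forces equal variances on Weeks 1 to 4. The model-based Week 4 standard error is then approximately a pooled value until the final ANCOVA, whose time point is unspecified. There is no effect if the unstructured model converges or the weekly variances are equal.

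The size rests on assumed SDs and complete data. A Week 4/Week 1 SD ratio of about 1.2 (420/360 = 1.17, or 1.2 itself) puts the one-sided 5% test at about 6.3% to 6.5%, with CI coverage of about 93%. A fall from 440 to 380 mL puts it at about 3.8%. Larger distortions need steeper changes in spread between Week 1 and Week 4 than anything in the documents suggests, and should not be taken as expected.

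Step 2 is a separate matter: without treatment-by-week there is no Week 4-specific contrast left to report.

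**What to change.** Amend SAP 4.11 before unblinding:

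- When the unstructured matrix is used, omit the separate participant random effect.
- On non-convergence, try heterogeneous Toeplitz, heterogeneous AR(1) and heterogeneous compound symmetry, in that order, keeping treatment-by-week and Kenward-Roger.
- Use the equal-variance versions only if all three fail.
- State the time point of the final ANCOVA.

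The cost is a few sentences and changes to the covariance and random-effect options in the model code. Each heterogeneous structure has three more variance parameters than its listed counterpart (7 against 4 for Toeplitz; 5 against 2 for the other two), still below the 10 of the unstructured matrix. The downside is a slightly higher chance of having to move to the next step, particularly if early closure leaves few participants.
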